5.7 Criteria for Removal from Study

CONFIDENTIAL

This document is confidential. Do not disclose or use except as authorized.

Participants will be removed from study when any of the criteria listed in Section 5.5 applies. The reason for study removal and the date the participant was removed must be documented in the study-specific case report form (CRF). Alternative care options will be discussed with the participant.

In the event of unusual or life-threatening complications, participating investigators must immediately notify the Principal Investigator:

[name] at [contact] or

6. EXPECTED TOXICITIES AND DOSING DELAYS/DOSE MODIFICATIONS

Dose delays and modifications will be made using the following recommendations. Toxicity assessments will be done using NCI Common Terminology Criteria for Adverse Events (CTCAE v4.02 from 9/15/2009) which is available at <http://ctep.cancer.gov/reporting//ctc.html>.

All adverse events experienced by participants will be collected from the time of the first dose of study treatment, through the study and until the final study visit. Participants continuing to experience toxicity at the off study visit may be contacted for additional assessments until the toxicity has resolved or is deemed irreversible.

CONFIDENTIAL

This document is confidential. Do not disclose or use except as authorized.

6.1 Anticipated Toxicities

Acute toxicities expected from conventional photon therapy administered alone, or with concurrent chemotherapy, to the pelvis or extended volume (pelvic and para-aortic nodal basins) are listed below. Because radiation will be administered to a smaller volume using proton beam, acute toxicities are expected to be delayed in onset and/or milder in severity. Recovery from acute side effects is expected over a 3-6 week period after the last treatment has been administered.

Acute (temporary) effects include:

Likely (more than 50% chance this will happen):

- Fatigue
- Cramps
- Frequent bowel movement
- Diarrhea
- Nausea
- Urinary frequency and urgency
- Burning with urination
- Vaginal irritation with itching and discharge
- Skin reaction (radiation dermatitis)
- Rectal irritation

Frequent (10-50% chance this will occur):

- Nausea (mild) and vomiting (rare) that is treatable with medications.
- Reduction in circulating blood counts including red cells which are important for carrying oxygen, platelets which are important for normal blood coagulation, and white cells which are important in fighting infection. If severe, changes in circulating blood counts may require blood transfusion, hospitalization, and medication intended to bring blood counts to normal levels.

Occasional (Between 1-10% chance this will occur):

- Dehydration and Electrolyte imbalances (changes in body salts) may occur in patients experiencing nausea, vomiting and diarrhea. This may not cause symptoms but sometimes causes fatigue, muscle weakness, muscle cramps, irregular heart beat or seizures. This can be severe and possibly life threatening, and may require hospitalization and intravenous treatment.

Delayed effects which may develop after completion of Proton beam radiation treatment include:

Frequent (10-50% chance this will occur):

- Leg lymphedema (swelling of legs due to a block in lymphatic flow)

CONFIDENTIAL

This document is confidential. Do not disclose or use except as authorized.

Occasional (Between 1-10% chance this will occur):

- Bowel obstruction requiring surgery to repair.
- Bowel injury
- Premature menopause: probable if ovaries have not been conserved surgically and removed to locations remote from the radiation target volumes.
- Bone fractures in the pelvis or spine
- Weight loss is slow and progressive and rarely exceeds 10% of pre-protocol treatment weight.

Rare (Less than a 1% chance this will occur):

- Appearance of radiation caused cancer in or next to the radiation site: very rare and usually observed 20 or more years after radiation treatment.
- Reduced bladder capacity with urinary frequency and urgency
- Potential injury to any/all normal tissues unavoidably irradiated
- Possible injury to liver and/or kidneys

6.1.2 Toxicity Management

Standard supportive therapies currently employed for radiation side effects will be administered in conventional dose, including anti-diarrheal medication (Imodium, Lomotil) anti-emetic medication (Ativan, Zofran, Reglan, Compazine, etc.) as required. No experimental medications or off-label medications will be employed. All supportive medications will be commercially available.

Outpatient intravenous hydration will be instituted for symptomatic dehydration or electrolyte imbalance induced by diarrhea (hypokalemia, hyponatremia).

6.2 Dose Modifications/Delays

6.2.1 Dose per proton teletherapy fraction will be 1.8 Gy (RBE) and will not be modified.

6.2.2 Treatment for uterine cancer patients will be suspended for thrombocytopenia with platelets <35,000 mcL or neutropenia with absolute neutrophil count <800/mcL or for abnormal bleeding or febrile neutropenia.

6.2.3 Treatment will resume at the same daily dose and fractionation schedule when circulating blood counts rise above these levels. Differential blood counts may be obtained twice weekly for uterine cancer patients, once weekly for cervix cancer patients commencing on or before fraction 8 of teletherapy.

CONFIDENTIAL

This document is confidential. Do not disclose or use except as authorized.

6.2.4 Treatment will be suspended for symptomatic dehydration and/or hyponatremia or hypokalemia requiring intravenous fluids. Treatment will resume as soon as parameters have normalized.

6.2.5 For cervical cancer patients getting chemotherapy concurrently with proton teletherapy, chemotherapy will be suspended for grade 3 neutropenia or grade 2 thrombocytopenia and resume when circulating counts have recovered above these levels. Daily radiation will not be suspended unless platelets fall below 35,000/mcL or absolute neutrophils fall less than 800/mcL.

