5.1 Pre-treatment Criteria

5.1.1 Day 1 proton beam teletherapy: Provided all laboratory determinations and imaging findings specified in section 3.1 are within the protocol eligibility requirements, no further pre-treatment criteria are established.

5.1.2 Subsequent proton beam teletherapy treatments 2-30: Maintenance of platelet count \geq 35,000/mcL and absolute neutrophil count \geq 800/mcL.

5.1.3 Uterine cancer patients who have received chemotherapy prior to proton therapy may have twice-weekly complete circulating blood counts commencing on or before treatment fraction 8. These labs will be ordered and monitored at the discretion of the treating physician.

5.1.4 Cervix cancer patients may have weekly complete blood counts commencing on or before treatment fraction 8. Cervix patients receiving concurrent chemotherapy will have weekly determination of serum electrolytes, renal function, Ca++, and Mg++. These labs will be ordered and monitored at the discretion of the treating physician.

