5.2.17 Uterine cancer patients will receive 3 brachytherapy fractions of 5 Gy each (15 Gy total) to the proximal vagina with dose specified at the vaginal mucosa (surface of the intra-

CONFIDENTIAL

This document is confidential. Do not disclose or use except as authorized.

vaginal applicator). The full length of the vagina will be treated employing a gradient dose distribution such that the distal anterior sub-urethral vagina receives 3 Gy with each brachytherapy treatment.

5.2.18 For patients with cystocoele or rectocoele or vaginal introital diameter <2.5 cm, vaginal brachytherapy will be administered in 5 fractions of 3 Gy mucosal dose to the proximal vagina using techniques and dose distributions as specified in 5.2.13-5.2.15. Uterine cancer patients will have the distal vaginal dose administered in 5 fractions of 1.8 Gy.

5.2.19 Maximum point dose to the bladder and rectum from brachytherapy will be calculated and recorded from CT dosimetry from one insertion with applicator in the vagina. These dose contributions will not be applied to dose constraints in sections 5.2.13.

5.2.20 Other Modalities or Procedures:

5.2.20a Uterine cancer patients may receive conventional chemotherapy prior to proton radiation, with the drugs, doses and routes of administration to be selected by their attending Gynecologic Oncologist or Medical Oncologist. Uterine cancer patients will not receive concurrent chemotherapy with protocol teletherapy. All pre-radiation chemotherapy will be with commercially available agents approved for use with uterine cancer patients.

5.2.20b Cervical cancer patients may receive concurrent adjuvant cytotoxic chemotherapy with the drugs, doses and routes of administration to be selected by their attending Gynecologic Oncologist or Medical Oncologist. All chemotherapy will be with commercially available agents approved for use with cervical cancer patients.

5.2.20c Experimental or non-standard chemotherapy regimens will not be administered to study participants. All chemotherapy agents administered prior to or during study participation will be FDA approved agents commercially available.

5.2.20d For patients developing cancer recurrence after protocol therapy, investigational agents will not be precluded from their subsequent care.

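### Section 6.2.2 names abnormal bleeding and febrile neutropenia as radiation holds for uterine patients only; cervical patients have no such stated hold, and the closing sentence of 6.2.5, read literally, contradicts 6.2.4

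*Combined protocol and SAP*

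**What the plan says.** Four provisions set radiation holds.

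- **5.1.2, all participants, from the second fraction:** "Subsequent proton beam teletherapy treatments 2-30: Maintenance of platelet count" of at least 35,000/mcL, and an absolute neutrophil count (ANC) of at least 800/mcL.
- **6.2.2, uterine patients:** "Treatment for uterine cancer patients will be suspended for thrombocytopenia with platelets" below 35,000/mcL or ANC below 800/mcL, "or for abnormal bleeding or febrile neutropenia".
- **6.2.4, no tumour-type limit:** "Treatment will be suspended for symptomatic dehydration and/or hyponatremia or hypokalemia requiring intravenous fluids".
- **6.2.5, cervical patients on concurrent chemotherapy:** "chemotherapy will be suspended for grade 3 neutropenia or grade 2 thrombocytopenia", and then, for radiation, "Daily radiation will not be suspended unless platelets fall below 35,000/mcL or absolute neutrophils fall less than 800/mcL".

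Section 6.2.3 governs restart after a hold and refers only to recovery of blood counts.

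On who may be irradiated during chemotherapy, 5.2.20a says "Uterine cancer patients will not receive concurrent chemotherapy with protocol teletherapy", while 5.2.20b says "Cervical cancer patients may receive concurrent adjuvant cytotoxic chemotherapy".

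**The concern.** The count limits are the same for both tumour types, but the two clinical-event holds are written for one type only, and no reason is given. Under 5.2.20a and 5.2.20b the group without them is the only group that may receive chemotherapy during radiation. If the omission is unintended, a foreseeable event has a planned response in one group and none in the other.

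The last sentence of 6.2.5 adds a second problem. Its *unless* construction lists two counts and nothing else. Taken at its word, it shuts out a bleeding hold and also the dehydration and electrolyte hold that 6.2.4 gives to everyone.

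What is at stake is clear instruction to treating staff. The statistical design is not involved.

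**Working it through.** **Step 1. Compare the holds by group.**

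| Trigger | Uterine | Cervical, concurrent chemotherapy | Cervical, no concurrent chemotherapy |
|---|---|---|---|
| Platelets <35,000/mcL or ANC <800/mcL | 5.1.2, 6.2.2 | 5.1.2, 6.2.5 | 5.1.2 |
| Dehydration, low sodium or low potassium needing IV fluids | 6.2.4 | 6.2.4, but excluded by a literal 6.2.5 | 6.2.4 |
| Abnormal bleeding, platelets ≥35,000/mcL | 6.2.2 | none stated; excluded by a literal 6.2.5 | none stated |
| Febrile neutropenia, ANC <800/mcL | 6.2.2 and the count rule | count rule | count rule |
| Febrile neutropenia, ANC ≥800/mcL, if it can occur | 6.2.2 | none stated; excluded by a literal 6.2.5 | none stated |

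The third row is the gap that the documents establish. The last row depends on how febrile neutropenia is defined. The protocol refers to CTCAE v4.02 without reproducing its text, so that row stays open.

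**Step 2. Look for the missing hold elsewhere.** Section 5.5 lists reasons to stop treatment. Its named adverse events include neither bleeding nor febrile neutropenia, and under 5.7 meeting any 5.5 criterion means removal from the study, which is not a short pause. The chemotherapy hold in 6.2.5 does not pause radiation. Section 13.3 permits a deviation to remove an immediate hazard, but it must be reported to the IRB. None of these is a stated radiation hold for either event.

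**Step 3. Check restart.** Section 6.2.3 resumes treatment when counts recover. A patient held for bleeding with adequate counts has no restart criterion. This already applies to uterine patients, so extending 6.2.2 alone would not be a complete repair.

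**Step 4. Count the patients an amendment could reach (14.2).**

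- Treated by October 2016: 9 uterine + 5 cervical = 14.
- The protocol's expected final cervical number: 22 × 5/14 = 7.9, about 8, as stated.
- Still to enrol: 22 − 14 = 8.
- Further cervical patients expected: 8 × 5/14 = 2.9, about 3 (equally, 8 − 5 = 3).
- The plan sets no tumour-type quota, so 0 to 8 are possible.

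The literal conflict in 6.2.5 reaches only those on concurrent chemotherapy, whose share is not given. At assumed shares of 100%, 50% and 0%, the expected number is 2.9, 1.4 and 0.

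These are head counts, not expected events. The documents give no rate for either event from which harm could be estimated.

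**The case against.** The strongest reply is that no competent physician would be misled. Section 6 introduces its rules as recommendations. Section 5.5 ties duration of therapy to tolerance and foresees delays for adverse events, with no tumour-type limit. Section 4.1 sends issues that would delay treatment to the Principal Investigator. Patients are examined weekly (9.2), and investigator judgement runs throughout. All of this stands. Pausing a bleeding cervical patient fits the protocol's general scheme, and the practical risk is small. But none of this text names the hold, and none removes the literal conflict between 6.2.5 and 6.2.4.

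The second reply is that the 6.2.5 sentence follows directly on chemotherapy count limits and was probably meant for counts only. That is the likelier intention, and this part is best treated as a drafting fault. The omission in 6.2.2 does not depend on it.

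Third, 3.1.3 can be read as allowing uterine patients chemotherapy alongside proton therapy, which would blur the contrast between the groups. Section 5.2.20a is explicit to the contrary, and the omission in 6.2.2 is there on either reading.

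A reader might infer that febrile neutropenia in cervical patients goes unmanaged. The documents do not support that: below 800/mcL it is held on the count. A reader might also infer that all of the roughly 8 cervical patients are exposed to harm. Five had already been treated, and the number who would meet an uncovered event is unknown.

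**Conclusion.** The point holds in a limited form. Section 6.2.2 gives the bleeding and febrile-neutropenia holds to uterine patients only, no other section gives them to cervical patients, and 6.2.5 as worded conflicts with 6.2.4. What is demonstrated as uncovered is abnormal bleeding with platelets at or above 35,000/mcL.

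It would go too far to say that the protocol requires radiation to continue in a bleeding cervical patient. That reading takes one sentence of 6.2.5 out of context and ignores the delays foreseen in 5.5.

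Severity is at the low end of minor. About 3 further cervical patients are expected, assuming that the tumour mix up to October 2016 continues. The primary endpoint compares dose volume histograms of treatment plans, which a pause in delivery does not change, so endpoint, sample size and power are unaffected. This is a cheap patient-safety improvement.

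**What to change.** Make three wording changes in one amendment.

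(a) In 6.2.2, delete the restriction to uterine cancer patients so that the holds cover all participants. Limit the bleeding trigger to bleeding that the treating physician judges clinically significant; otherwise minor bleeding after hysterectomy could force a hold.

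(b) In the last sentence of 6.2.5, say that the limits of 35,000/mcL and 800/mcL apply to pausing radiation for blood counts alone, and that the holds in 6.2.2 and 6.2.4 still apply.

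(c) In 6.2.3, state that treatment resumes when counts have recovered and the bleeding or fever has resolved.

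The cost is an amendment with IRB approval. No new tests or data collection are needed. The downside is possible treatment breaks among the cervical patients still to be enrolled; their frequency and length cannot be derived from the documents.

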7. DRUG FORMULATION AND ADMINISTRATION: N/A

8. CORRELATIVE/SPECIAL STUDIES: N/A

9. STUDY CALENDAR

9.1 Baseline hematologic evaluations are to be conducted within 2-weeks prior to study entry. Scans must be done \leq 10 weeks prior to study entry.

9.2 Patients will be interviewed and examined weekly during treatment.

9.3 Routine surveillance follow-up will be: 3, 6, 9, 12, 15, 18, 21, 24, 28, 32, 36, 42, 48, 54 and 60 months (+/- 4 weeks) following adjuvant radiation treatment.

CONFIDENTIAL

This document is confidential. Do not disclose or use except as authorized.

9.4 Study Calendar/Required Data

Tests and Observations	At Study Entry	During Treatment	At Follow Up (1)
Informed Consent	x		
History	x		x
Concurrent Meds	x	x	x
Physical Exam (2)	x	x	x
Pelvic Exam (3)	x	x	x
CBC with diff, PLT (4)	x	x	
Serum Chemistries (5)	x	x	
Toxicity and AE evaluation	x	x	x
Radiological imaging (6)	x		x
Quality of Life (7)	x		x

Notes:

- (1) Follow up schedule (+/- 4 weeks for each time point): every 3 months for 2 years; every 4 months to year 3; every 6 months until year 5.
- (2) Physical includes, weight, vitals, performance status required at baseline. For weekly on-treatment and follow up visits, physical exam will be performed as pertinent at the discretion of the treating physician, and includes weight. .
- (3) Pelvic Exam pre-study, during vaginal brachytherapy (typically week 6 of treatment) and at each follow up visit
- (4) Study entry labs for pre-treatment must be done within 14 days of study entry. Labs may be repeated twice weekly for uterine cancer patients, once weekly for cervix cancer patients during treatment to ensure maintenance of platelets >35,000mcL and ANC >800mcL. These labs are ordered and monitored at the discretion of the treating physician.
- (5) Required chemistries are: Albumin, Alk Phos, T bili, BUN, bicarbonate, chloride, creatinine, glucose, LDH, phosphorus, potassium, total protein, SGOT, SGPT, sodium, calcium, magnesium. These will be ordered and monitored at the discretion of the treating physician.
- (6) Contrast enhanced CT scan of the chest, abdomen and pelvis pre-study (\leq 10 weeks of study entry) and in post treatment, twice per year to year 3.
- (7) Quality of Life will be assessed using the FACT-En Version 4 (Appendix 2) instrument for uterine patients and the FACT-Cx Version 4 (Appendix 3) instrument for cervix patients. QOL will be assessed at study entry, and at 6, 12, 24, 36, 48, and 60 months (+/- 4 weeks) after protocol therapy.

10. MEASUREMENT OF EFFECT: Participants are excluded if they have measurable disease following hysterectomy. (3.2.2, 3.2.3)

10.1 Progression-Free Survival

Progression-Free Survival (PFS) is defined as the duration of time from start of treatment to time of objective disease progression at any site as detected by symptomatic recurrence or routine surveillance follow-up physical examination or imaging as described in the Study Calendar (Section 9).

CONFIDENTIAL

This document is confidential. Do not disclose or use except as authorized.

10.1.1 Following protocol therapy, patients will be seen in routine surveillance follow- up at 3, 6, 9, 12, 15, 18, 21, 24, 28, 32, 36, 42, 48, 54 and 60 months

10.1.2 At each follow-up interval history, weight and vital signs will be obtained, and general physical examination including pelvic examination will be performed.

10.1.3 CT scans of the chest, abdomen, and pelvis will be obtained twice per year post treatment to year 3.

10.1.4 For this protocol, routine blood work will not be obtained in asymptomatic patients except as required for imaging contrast administration.

10.2 Pattern of Recurrence

Local recurrence is defined as cancer detected at any time after initiation of treatment that lies within the volume of target tissue undergoing adjuvant proton beam teletherapy.

Marginal Recurrence is defined as cancer detected at any time following initiation of adjuvant proton beam teletherapy that lies within 1 cm of tissue that receives 90% of the daily prescribed radiation dose.

Distant Recurrence is defined as cancer which has spread by hematogenous dissemination or peritoneal dissemination to sites spatially remote from the irradiated target volume.

10.3 Quality of Life

Quality of life will be assessed at 6, 12, 24, 36, 48, 60 months following protocol therapy.

QOL will be assessed using the FACT-En Version 4 instrument for uterine patients and the FACT-Cx Version 4 for cervix patients.

11. ADVERSE EVENT REPORTING REQUIREMENTS

11.1 General

Adverse event collection and reporting is a routine part of every clinical trial. This study will use the descriptions and grading scales found in the NCI Common Terminology Criteria for Adverse Events (CTCAE) version 4.02 9/15/2009 that is available at <http://ctep.cancer.gov/reporting//ctc.html>.

CONFIDENTIAL

This document is confidential. Do not disclose or use except as authorized.

Information on all adverse events, whether reported by the participant, directly observed, or detected by physical examination, laboratory test or other means, will be collected, recorded, followed and reported as described in the following sections.

Adverse events experienced by participants will be collected and reported from initiation of study treatment, throughout the study, and within 60 months of the last dose of study medication. Participants who experience an ongoing adverse event or related to a study procedures and/or study medication beyond 60 months will continue to be contacted by a member of the study team until the event is resolved, stabilized, or determined to be irreversible by the participating investigator.

Participants should be instructed to report any serious post-study event(s) that might reasonably be related to participation in this study. The investigator should notify the IRB and any other applicable regulatory agency of any unanticipated death or adverse event occurring after a participant has discontinued or terminated study participation that may reasonably be related to the study.

11.2 Definitions

11.2.1 Adverse Event (AE)

An adverse event is any undesirable sign, symptom or medical condition or experience that develops or worsens in severity after starting the first dose of study treatment or any procedure specified in the protocol, even if the event is not considered to be related to the study.

Abnormal laboratory values or diagnostic test results constitute adverse events only if they induce clinical signs or symptoms or require treatment or further diagnostic tests.

11.2.2 Serious adverse event (SAE)

A serious adverse event is an undesirable sign, symptom, or medical condition which:

- is fatal or life-threatening;
- requires or prolongs inpatient hospitalization;
- results in persistent or significant disability/incapacity;
- constitutes a congenital anomaly or birth defect; or
- jeopardizes the participant and requires medical or surgical intervention to prevent one of the outcomes listed above.

Events **not** considered to be serious adverse events are hospitalizations for:

CONFIDENTIAL

This document is confidential. Do not disclose or use except as authorized.

- routine treatment or monitoring of the studied indication, not associated with any deterioration in condition, or for elective procedures
- elective or pre-planned treatment for a pre-existing condition that did not worsen
- emergency outpatient treatment for an event not fulfilling the serious criteria outlined above and not resulting in inpatient admission
- respite care

